2 PROTOCOL SYNOPSIS

Title A Phase 2, Randomized, Double-blind, Active-controlled, Dose-ranging,

Parallel-design Study of the Efficacy and Safety of VX-548 in Subjects With Painful

Diabetic Peripheral Neuropathy

Brief Title Evaluation of Efficacy and Safety of VX-548 for Painful Diabetic Peripheral

Neuropathy

Clinical Phase and Clinical Study Type

Clinical Phase and Phase 2, efficacy and safety

Objectives Primary Objectives

- To evaluate the efficacy of three VX-548 doses in treating subjects with painful diabetic peripheral neuropathy (DPN)
- To evaluate the safety and tolerability of VX-548

[figure not shown]

Endpoints Primary Endpoint

 Change from baseline in the weekly average of daily pain intensity on a numeric pain rating scale (NPRS) at Week 12

Secondary Endpoints

- Change from baseline in the weekly average of the Daily Sleep Interference Scale (DSIS) at Week 12
- Proportions of subjects with ≥30%, ≥50%, and ≥70% reductions from baseline in the weekly average of daily pain intensity on the NPRS at Week 12
- Proportion of subjects categorized as much improved or very much improved at Week 12 on the patient global impression of change (PGIC) assessment
- Safety and tolerability based on the incidence and type of adverse events (AEs) and changes from baseline in clinically significant laboratory test results, vital signs, and ECGs at each visit

Number of Subjects Approximately 175 subjects

Study Population

Male and female subjects 18 through 80 years of age, inclusive, with presence of bilateral pain in lower extremities due to DPN for at least 1 year, and weekly average NPRS pain score of ≥4 with limited variation in the Run-in Period

Investigational Drug

Active substance: VX-548 Activity: Na_v1.8 inhibitor

Strength and route of administration: 23-mg tablets and matching placebo for oral

administration

Reference Drug

Active substance: Pregabalin

Activity: Calcium channel (alpha₂-delta site) inhibitor

Strength and route of administration: 100-mg capsules and matching placebo for oral

administration

[figure not shown]
Study Duration

Excluding the Screening Period (which includes a 7-day Run-in Period), each subject will participate in the study for approximately 14 weeks: a 12-week Treatment Period and a Safety Follow-up Visit 14 (± 2) days after the end of the Treatment Period.

Study Design

This is a Phase 2, randomized, double-blind, active-controlled, dose-ranging, 4-arm, parallel-design study. Subjects who meet eligibility criteria during Screening Visits 1 and 2 will enter a 7-day Run-in Period to establish their baseline NPRS pain score. Subjects with a baseline average NPRS score of ≥4 points with limited variation (SD <25% of mean) will be eligible for the 12-week Treatment Period followed by a Safety Follow-up Visit (Figure 2-1).

Figure 2-1 VX21-548-103 Study Design

N: number of subjects

At the end of the Treatment Period (Week 12), subjects will taper off capsule (pregabalin reference or matched placebo) study drug for 7 days.

A total of approximately 175 subjects will be randomized 2:2:1:2 to 4 treatment arms: VX-548 (high, mid, or low dose) or pregabalin (reference arm) (Table 2-1). Randomization will be stratified by sex (female and male) and body mass index (≥30 and <30 kg/m²). To maintain the blind, all subjects will receive the same number of tablets once daily (qd) in the morning and the same number of capsules 3 times per day in a double-dummy design. After the Treatment Period, subjects will taper off capsule (pregabalin reference or matched placebo) study drug for 7 days (4 days of dosing every 12 hours, then 3 days of dosing qd), and the Safety Follow-up Visit will occur an additional 7 (± 2) days later.

Table 2-1 VX21-548-103 Treatment Arms

| | | Number of Subjects |
|--------------------|-------------|--------------------|
| Treatment | Active Dose | (Planned) |
| VX-548 (high dose) | 69 mg qd | 50 |
| VX-548 (mid dose) | 46 mg qd | 50 |
| VX-548 (low dose) | 23 mg qd | 25 |
| Pregabalin | 100 mg tid | 50 |

qd: once daily; tid: 3 times per day

Note: To maintain the blind, all subjects will receive the same number of tablets and the same number of capsules at the same respective frequency (i.e., qd for tablets and tid for capsules during the Treatment Period) in a double-dummy design.

Subjects will stop taking pain medications (including pregabalin, if applicable), except acetaminophen (500 mg), for at least 14 days before the first dose of study drug.

Acetaminophen will be permitted as a pain rescue medication as needed (prn) throughout the study. Subjects will be permitted to take 500 mg every 4 to 6 hours prn, up to a maximum of 2500 mg in any 24-hour period. Subjects will record rescue medication use, and their current pain score on the NPRS immediately before each administration of rescue medication.

Assessments

Efficacy: 11-point NPRS, DSIS, PGIC, use of rescue medication, and

Safety: AEs; clinical laboratory assessments; clinical evaluation of vital signs, ECGs, and physical examination; and Columbia Suicide Severity Rating Scale

Statistical Analyses

The primary efficacy endpoint is the change from baseline in the weekly average of the daily pain intensity on an NPRS at Week 12. The primary analysis will be a within-group comparison in any VX-548 dose group.

The sample size is based on the primary analysis of the primary endpoint. With 37 evaluable subjects in the VX-548 high or mid dose group and 18 evaluable subjects in the VX-548 low dose group, there is more than 90% power in any VX-548 dose group to detect a mean change from baseline of 3 with a single group *t*-test at the 2-sided 0.05 significance level, assuming the SD is 2.3. With an evaluable sample size of 37, a 2-sided 95% CI for the mean change from baseline in the high or mid dose group will extend 0.77 on either side of the observed mean, assuming the CI is based on the *t*-statistic and the observed SD is 2.3. Under the same assumptions and an evaluable sample size of 18, a 2-sided 95% CI for the mean change from baseline in the low dose group will extend 1.14 on either side of the observed mean. To account for a 25% dropout rate, 50 subjects each will be enrolled in the VX-548 high dose, VX-548 mid dose, and the pregabalin groups; 25 subjects will be enrolled in the VX-548 low dose group. The total sample size is 175 subjects.

The primary efficacy analysis will be based on a mixed-effects model for repeated measures (MMRM), with change from baseline in weekly average of daily pain intensity score as the dependent variable; and fixed effects of treatment group, time (categorical), treatment group-by-time interaction, baseline weekly average of daily pain intensity, and baseline weekly average of daily pain intensity-by-time interaction. The least squares (LS) mean change from baseline at Week 12 for each

group will be presented with the corresponding SE, and the corresponding 95% CI and P value.

3 SCHEDULE OF ASSESSMENTS

Schedules of assessments are in Table 3-1 and Table 3-2.

Table 3-1 Study VX21-548-103: Screening Period (Including 7-Day Run-in Period)

| | Day -35 to Day -9 | Day -8 | Day -7 to Day -1 | |
|--|----------------------|-----------------------------------|------------------|---|
| Event/Assessment ^a | Screening Visit 1 | Screening Visit 2 ^b | Run-in Period | Comments |
| Informed consent | X | | | Must be obtained before performing any study-related procedures. Remote consent may be used if permitted by local regulations; Section 13.2.3. |
| Clinic or home health visit | Х | | | Subjects will have the option to complete this visit in the clinic or to have a home health visit. Home health visits are only an option if permitted by local regulations. Section 9.1.1.1. |
| Telemedicine video conference or telephone contact | х | | | A consultation between the subject and investigator or qualified delegate (LIP) must be performed within 2 business days after home health visit. Required only for subjects who have a home health visit; not required for subjects who have a clinic visit; Section 9.1.5 |
| Clinic visit | | X | | |
| Discontinue specified medications | X | Х | X | Section 9.4 |
| Demographics | X | | | |
| Medical history | X | | | |
| Weight, height, and BMI | X | | | Weight and height will be measured with shoes off. |
| Vital signs | X | | | Vital signs will be collected after the subject has been at rest (seated or supine) for at least 5 minutes; Section 11.5.3 |
| Complete physical examination | | X | | At times other than Screening Visit 2, symptom-directed PEs may be performed at the discretion of the investigator or health care provider; Section 11.5.3 |
| Standard 12-lead ECG | | Х | | Standard 12-lead ECGs will be performed in triplicate after subjects have been at rest (supine) for at least 5 minutes; Section 11.5.4 |
| Serum β-hCG | X | | | All biologically female subjects; Section 11.5.2 |
| Serum FSH | X | | | Suspected postmenopausal female subjects only; Section 11.5.2 |
| Serology (HBsAg, HCV Ab, and HIV-1/HIV-2 Abs) | X | | | Section 11.5.2 |
| Serum chemistry | X | | | |
| Hematology | X | | | |
| Coagulation | X | | | |
| HbA1c | X | | | |
| Thyroid function test | X | | | |
| Vitamin B12 | X | | | 1 |
| Urinalysis | X | | | 1 |

Table 3-1 Study VX21-548-103: Screening Period (Including 7-Day Run-in Period)

| | Day -35 to Day -9 | Day -8 | Day -7 to Day -1 | |
|---|----------------------|--|----------------------------|--|
| Event/Assessment ^a | Screening Visit 1 | Screening Visit 2 ^b | Run-in Period | Comments |
| Urine drug test | Х | (X) | | Subjects who have a positive screen for opioids (acute use only) or marijuana may repeat the test at Screening Visit 2, as noted by (X); the second test must be at least 7 days (marijuana) or at least 3 days (opioid) after the first. Section 11.5.2 |
| Urine alcohol test | X | | | Section 11.5.2 |
| Pain assessment training | | X | | Section 9.1.1.1 |
| e-diary and ePRO training and device distribution | | X | | |
| NPRS via daily e-diary | | | X | Each morning, subjects will record their average daily NPRS score from the previous 24 hours. Subjects will also report their current pain score immediately before each administration of rescue medication, if applicable. Section 11.3. |
| DSIS via daily e-diary | | | X | Each morning, subjects will report on the previous night's sleep using the DSIS; Section 11.3. |
| Rescue medication use | | | X | Subjects will record NPRS pain score immediately before each administration and record date and time of administration in an e-diary; Section 11.3 |
| Medication review | Continuous fro | nuous from signing of ICF through Follow-up Visit | | All medications taken within 14 days before Screening Visit 1 and selected prior medications taken earlier; Section 9.5 |
| Treatment and procedures review | Continuous fro | m signing of Follow-up V | ICF through Safety isit | |
| Adverse events | | from signing fety Follow-u | of ICF through p Visit | |

β-hCG: beta-human chorionic gonadotropin; BMI: body mass index; DSIS: Daily Sleep Interference Scale; e-diary: electronic diary; ePRO: electronic patient-reported outcome; FSH: follicle-stimulating hormone; HbA1c: hemoglobin A1c (glycosylated hemoglobin); HBsAg: hepatitis B surface antigen; HCV Ab: hepatitis C virus antibody; HIV-1/HIV-2 Abs: antibodies against human immunodeficiency viruses 1 and 2; ICF: informed consent form; NPRS: numeric pain rating scale; PE: physical examination

When assessment time points coincide, assessments will be performed in the following order: vital signs, 12-lead ECG, PE, and blood sample collection.

b Screening Visit 2 may occur only after laboratory results from Screening Visit 1 are available and have established subject eligibility to continue study participation. Screening Visit 2 will be considered as Day -8.

Protocol VX21-548-103, Version 3.0 Page 9 of 60

Table 3-2 Study VX21-548-103: Treatment Period and Safety Follow-up Visit

| | | | Tı | eatment Per | iod | _ | | | | Safety Follow-up | |
|--|--------|-----------|------------|-------------|------------|------------|---------|--------------------|--------------------|-------------------------------------|---|
| | | Week 1 | Week 3 | Week 5 | Week 7 | Week 9 | Week 12 | ETT | | Visit 14 (± 2) Days After End of | |
| Event/Assessment ^a | Day 1b | (± 1 Day) | (± 3 Days) | (± 3 Days) | (± 3 Days) | (± 3 Days) | | Visit ^c | Taper ^d | Treatment Period | Comments |
| Clinic visit | X | X | (| X | (| (| X | X | | X | |
| Clinic or home health visit | | | Х | | Х | Х | | | | | Subjects will have the option to complete these visits in the clinic or to have a home health visit. Home health visits are only an option if permitted by local regulations; Section 9.1.1 |
| Telemedicine video conference or telephone contact | | | х | | х | х | | | | | A consultation between the subject and investigator or qualified delegate (LIP) must be performed within 2 business days after home health visit. Required only for subjects who have a home health visit; not required for subjects who have a clinic visit; Section 9.1.5 |
| Randomization | Х | | | | | | | | | | Occurs after eligibility is confirmed, including criteria for average NPRS during 7-day Run-in Period. |
| Weight | X | X | | X | | | X | X | | | Weight will be measured with shoes off. |
| Vital signs | х | x | x | x | x | x | Х | X | | | Vital signs will be collected after the subject has been at rest (seated or supine) for at least 5 minutes and before 12-lead ECG assessment or blood sampling. At the Day 1 and Week 5 visits, vital signs will be collected predose only; Section 11.5.3. |
| Standard 12-lead ECG | Х | X | | X | | | X | X | | | Standard 12-lead ECGs will be performed in triplicate after subjects have been at rest (supine) for at least 5 minutes; 12-lead ECGs will be done after taking vital signs and before any procedures that may affect |

Protocol VX21-548-103, Version 3.0 Page 10 of 60

Table 3-2 Study VX21-548-103: Treatment Period and Safety Follow-up Visit

| | Treatment Period Safety Follow-up | | | | | | | | | | |
|-------------------------------|-----------------------------------|-----------------------|------------|------------|------------|-------------|------------|--|--------------------|----------------------------------|--|
| | | Week 1 | Week 3 | Week 5 | Week 7 | Week 9 | Week 12 | TO TO TO | | Visit 14 (± 2) Days | |
| Event/Assessment ^a | Day 1 ^b | (± 1 Day) | (± 3 Days) | (± 3 Days) | (± 3 Days) | (± 3 Days) | (± 3 Days) | ETT Visit ^c | Taper ^d | After End of Treatment Period | Comments |
| | | (=124) | (LUDinys) | (±0Days) | (#DDays) | (20 Days) | (#DDays) | VISIC | Tapes | Tremment Terror | heart rate (e.g., blood sampling). At the Day 1 and Week 5 Visits, ECGs will be collected predose and at 2 and 4 hours postdose. At all other visits, ECGs will be collected during the visit without regard to dosing; Section 11.5.4. |
| Complete PE | X | | | | | | | | | | Section 11.5.3 |
| Abbreviated PE | | | | | | As applicab | le | | | | Symptom-directed PEs will occur at any time during the study if triggered by AEs or if deemed necessary by the investigator; Section 11.5.3. |
| BSTK evaluation | X | | | | | | X | X | | | Section 11.4 |
| NPRS via daily e-diary | | Day 1 through Week 12 | | | | | | Each morning, before the first daily dose, subjects will record their average daily NPRS score from the previous 24 hours. Subjects will also report their current pain score immediately before each administration of rescue medication, if applicable. Section 11.3 | | | |
| DSIS via daily e-diary | | | | | | | | Each morning, before the first daily dose, subjects will report on the previous night's sleep using the DSIS. Section 11.3 | | | |
| PGIC | | X | | X | | | X | X | | X | Section 11.3 |
| | | | | | | | | | | | |
| C-SSRS | X | X | | X | | | X | X | | X | Section 11.5.5 |
| Urinalysis | X | | X | | | X | X | | | | Section 11.5.2 |
| Drug and alcohol testing | Xe | | X | | | X | X | X | | |] |
| Pregnancy test ^f | urinee | urine | urine | urine | urine | urine | serum | serum | | urine | |

Table 3-2 Study VX21-548-103: Treatment Period and Safety Follow-up Visit

| | | | Tı | reatment Per | iod | | | | | Safety Follow-up | |
|--|--------------------|---|----------------------|------------------------------|----------------------------|-------------------------|-----------------------|---------------------------|--------------------|---|---|
| Event/Assessment ^a | Day 1 ^b | Week 1 (± 1 Day) | Week 3 (± 3 Days) | Week 5 (± 3 Days) | Week 7 (± 3 Days) | Week 9 (± 3 Days) | Week 12 (± 3 Days) | ETT Visit ^c | Taper ^d | Visit 14 (± 2) Days After End of Treatment Period | Comments |
| Coagulation | | | | | | | X | X | | | |
| Hematology | X | | X | | | X | X | X | | | |
| Serum chemistry | X | | X | | | X | X | | | | |
| HbA1c | | | | | | | X | X | | | |
| DNA blood sample (optional) | X | | | | | | | | | | Optional DNA sample may be collected at any time on Day 1 after subject randomization (Section 11.4) |
| Nf-L biomarker sample | X | X | | X X | | | X | X | | | Section 11.4 |
| Pain assessment training refresher Study drug administration | The last | ough Week 12 first dose of table ering regimen | daily doses w | n the morning vill be admini | stered at the morning of t | clinic. he Week 12 V | Visit. The | | x | | Section 9.1.1.1 Subjects will record the date and time of each dose administration in an e-diary. To maintain the blind, subjects will receive the sam number of tablets and/or capsules at the same respective frequencies in each treatment group; Section 9.6 |
| Study drug count | | X | X | X | X | X | X | х | | X | G F , |
| Rescue medication use | |   | | rom Day 1 thi | 1 |   | ı | | | | Subjects will record NPRS pain score immediately before each administration and record date and time of administration in an e-diary Section 11.3 |

Protocol VX21-548-103, Version 3.0 Page 12 of 60

Table 3-2 Study VX21-548-103: Treatment Period and Safety Follow-up Visit

| | Treatment Period Safety Follow-up | | | | | | | | | | |
|---------------------------------------|-----------------------------------|--|---------|--------------|----------------|--------------|----------------|-----------|----|-------------------------------------|--|
| | | Week 1 | Week 3 | Week 5 | Week 7 | Week 9 | Week 12 | ETT | | Visit 14 (± 2) Days After End of | |
| Event/Assessment ^a | Day 1 ^b | Day 1 ^b (± 1 Day) (± 3 Days) Visit ^c Taper ^d Treatment Period | | | | | | | | Comments | |
| Medications review | | | Continu | ous from sig | ning of the IC | F through th | e Safety Follo | ow-up Vis | it | | |
| Concomitant treatments and procedures | | Continuous from signing of the ICF through the Safety Follow-up Visit | | | | | | | | | |
| Adverse events | | | Continu | ous from sig | ning of the IC | F through th | e Safety Follo | ow-up Vis | it | | |

; BSTK: bedside sensory testing kit; C-SSRS: Columbia Suicide Severity Rating Scale; DSIS: Daily Sleep Interference Scale; e-diary: electronic diary; ETT: early termination of treatment; HbA1c: hemoglobin A1c (glycosylated hemoglobin); ICF: informed consent form; LIP: licensed independent practitioner; Nf-L: neurofilament light chain; NPRS: numeric pain rating scale; PE: physical examination; PGIC: patient global impression of change; q12h: every 12 hours; qd: once daily; tid: 3 times per day

- At each visit, documentation of the previous day's NPRS score by the subject should be confirmed before performing any assessments. When assessment time points coincide, assessments will be performed in the following order: patient-reported outcomes (e.g., NPSI), vital signs, 12-lead ECG, PE, and blood sample collection.
- On Day 1 and the Week 5 visit, all assessments must be completed before the first daily dose of study drug, except for the postdose PK and ECG sampling.
- If a subject prematurely discontinues study treatment, an ETT Visit should be scheduled as soon as possible after the subject decides to terminate study treatment; the subject will be encouraged to complete the capsule (pregabalin reference or matched placebo) study drug taper. Subjects who prematurely discontinue treatment will be encouraged to stay in the study, including completing the daily diaries and returning for clinical visits to complete study efficacy assessments (i.e., NPRS, PGIC, DSIS, NPSI, use of rescue medication, and SF-MPQ-2). These subjects will also be required to complete the Safety Follow-up Visit. If the ETT Visit occurs 14 days or later following the last tablet of study drug, then the ETT Visit will replace the Safety Follow-up Visit, and a separate Visit will not be required.
- d After the Treatment Period (capsule dosing tid), subjects will taper off capsule (pregabalin reference or matched placebo) study drug as follows: 4 days of dosing q12h, then 3 days of dosing qd in the evening.
- e Results from the Day 1 urine pregnancy, drug, and alcohol tests are required before the first dose.
- f Pregnancy tests will only be performed for female subjects of childbearing potential.

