7.2 Secondary Endpoints

- Change from baseline in the weekly average of the Daily Sleep Interference Scale (DSIS) at Week 12
- Proportions of subjects with ≥30%, ≥50%, and ≥70% reductions from baseline in the weekly average of daily pain intensity on the NPRS at Week 12
- Proportion of subjects categorized as much improved or very much improved at Week 12 on the patient global impression of change (PGIC) assessment
- Safety and tolerability based on the incidence and type of AEs and changes from baseline in clinically significant laboratory test results, vital signs, and ECGs at each visit

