11.5.2 Clinical Laboratory Assessments

Blood and urine samples will be analyzed at a central laboratory, unless otherwise specified. On Day 1, blood samples will be collected before the first dose of the study drug. At all other scheduled visits, these samples will be collected at any time during the visit.

Laboratory test results that are abnormal and considered clinically significant will be reported as AEs (see Section 13.1).

The safety laboratory test panels are shown in Table 11-2.

Table 11-2 Safety Laboratory Test Panels

| Serum Chemistry | Hematology | Urinalysis ^a |
|----------------------------------|---------------------------------------|-------------------------|
| Glucose | Hemoglobin | Urobilinogen |
| Blood urea nitrogen ^b | Platelets | Urine protein |
| Creatinine | Leukocytes | pН |
| Sodium | Differential (percent): | Urine blood |
| Potassium | Eosinophils | Specific gravity |
| Calcium | Basophils | Urine ketones |
| Chloride | Neutrophils | Urine bilirubin |
| Magnesium | Lymphocytes | Urine glucose |
| Bicarbonate | Monocytes | |
| Phosphate | | |
| Total bilirubin | | |
| Direct bilirubin | | |
| Alkaline phosphatase | | |
| Aspartate transaminase | | |
| Alanine transaminase | | |
| Lipase | Coagulation | |
| Gamma-glutamyl transferase | Activated partial thromboplastin time | |
| Protein | Prothrombin time | |
| Albumin | Prothrombin time International | |
| Creatine kinase | Normalized Ratio | |
| Urate | | |

^a If urinalysis results are positive for protein or blood, microscopic examination of urine will be performed and results provided for leukocytes, erythrocytes, crystals, bacteria, and casts.

Clinical laboratory assessments from Screening Visit 1 must have no clinically significant findings that preclude participation in the study, as judged by the investigator, for a subject to proceed to Screening Visit 2 and to receive study drug on Day 1.

Additional tests at screening: The following additional tests will be performed during screening (at Screening Visit 1) to assess eligibility:

- Serum β-human chorionic gonadotropin (β-hCG) test for all biologically female subjects
- Serum follicle-stimulating hormone (FSH) for female subjects who are suspected to be
 postmenopausal; for a subject to be considered of nonchildbearing potential, the serum FSH
 levels will be within the laboratory's range for postmenopausal females

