11.5.3 Physical Examinations and Vital Signs

A PE of all body systems will be performed at Screening Visit 2 and Day 1. At other visits, symptom-directed PEs can be performed at the discretion of the investigator or healthcare provider. Vital signs assessments will be performed at Screening Visit 1 and at each clinic or home health visit.

A PE includes a review of the following systems: head, neck, and thyroid; eyes, ears, nose, and throat (EENT); respiratory; cardiovascular; lymph nodes; abdomen; skin; musculoskeletal; and neurological. Breast, anorectal, and genital examinations will be performed when medically

indicated. After screening, any clinically significant abnormal findings in a PE will be reported as AEs. If there is a PE finding during a home visit, depending on its severity and at investigator discretion, the subject may be instructed to have a PE or other evaluation in the clinic.

Vital signs include blood pressure (systolic and diastolic), temperature, pulse rate, and respiration rate. The subject will be instructed to rest (seated or supine) for at least 5 minutes before vital signs are assessed.

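### As Table 3-2 reads, serum chemistry and urinalysis are the only assessments marked at Week 12 but not at the Early Termination of Treatment (ETT) Visit, so early stoppers have no protocol-scheduled end-of-treatment chemistry

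*Protocol*

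**What the plan says.** Protocol Section 3, Table 3-2, sets the laboratory schedule. Its columns run Day 1, Weeks 1, 3, 5, 7, 9 and 12, ETT, Taper, Safety Follow-up, Comments.

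- Serum chemistry: "Serum chemistry | X | | X | | | X | X", with nothing under ETT or Safety Follow-up.
- Urinalysis: "Urinalysis | X | | X | | | X | X | | | | Section 11.5.2". The cells after the Week 12 mark are empty up to the comment.
- Hematology: "Hematology | X | | X | | | X | X | X". The last mark is ETT.
- Coagulation: "Coagulation | | | | | | | X | X". The marks are Week 12 and ETT. HbA1c has the same pattern.

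Section 11.5.2 says that "The safety laboratory test panels are shown in Table 11-2". That table puts ALT, AST, bilirubin, creatinine, creatine kinase and lipase under serum chemistry. Section 7.2 makes safety a secondary endpoint through AEs and "changes from baseline in clinically significant laboratory test results, vital signs, and ECGs at each visit".

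Under Section 9.1.4, subjects who stop treatment are encouraged to return for efficacy assessments and must attend the Safety Follow-up Visit. An ETT Visit falling within a week of a scheduled Treatment Period visit replaces that visit. SAP Section 9.4.2 summarizes how many subjects meet the Appendix E thresholds during the treatment-emergent (TE) period.

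**The concern.** Hematology and chemistry share the same treatment-period schedule and the same SAP analysis windows. They differ only at ETT, and no reason is given. ETT is also where toxicity cases go: Section 9.7 allows no dose modification and sends unacceptable toxicity to discontinuation under Section 9.1.4.

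The SAP's liver, creatinine, CK and lipase thresholds all need the chemistry panel. A subject with no value near the time of stopping cannot be counted as abnormal at that time. The planned summaries may therefore under-count abnormal chemistry in the group where it is of most interest.

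**Working it through.** The plan states no figure on this point. The check is a reading of the table, then a sizing from the plan's dropout allowance.

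**1. Reading the table.** Each row was matched to the column headers.

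| Row | Day 1 | Wk 3 | Wk 9 | Wk 12 | ETT | Safety Follow-up |
|---|---|---|---|---|---|---|
| Serum chemistry | X | X | X | X | blank | blank |
| Urinalysis | X | X | X | X | blank | blank |
| Hematology | X | X | X | X | X | blank |
| Coagulation | blank | blank | blank | X | X | blank |
| HbA1c | blank | blank | blank | X | X | blank |
| Drug and alcohol testing | X | X | X | X | X | blank |

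Sixteen legible rows carry a Week 12 visit mark. Fourteen also carry an ETT mark: clinic visit, weight, vital signs, ECG, sensory testing, PGIC, C-SSRS, drug and alcohol testing, pregnancy test, coagulation, hematology, HbA1c, Nf-L and drug count. The two that do not are serum chemistry and urinalysis.

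**2. Looking for the panel elsewhere.**

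- The Safety Follow-up column has no chemistry.
- Section 9.1.4 and Table 3-2 footnote c list efficacy assessments for those who stay on after stopping.
- Section 11.5.2 adds no chemistry at ETT. It allows further tests only on clinical judgment.
- Section 9.1.4 lets an ETT Visit replace a Week 3, 9 or 12 visit, each of which has chemistry. It does not say whether that draw is still made.

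**3. Size.** Inputs are 175 subjects and 25% dropout (Protocol Section 12.1), a 12-week (84-day) Treatment Period, and target days 22 (Week 3) and 64 (Week 9) from SAP Appendix A. All dropout is taken as treatment discontinuation, which makes this an upper bound.

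- Early stoppers: 175 × 0.25 = 43.75, about 44.
- Before the Week 3 draw, even stopping: 43.75 × 22/84 = 11.5.
- Before the Week 3 draw, constant hazard: 175 × (1 − 0.75^(22/84)) = 12.7.
- Between Day 22 and Day 64, even stopping: 43.75 × 42/84 = 21.9. Their last scheduled value is Week 3.
- After Day 64, even stopping: 43.75 × 20/84 = 10.4. Their last scheduled value is Week 9.

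| Dropout | Early stoppers | Before Week 3, even | Before Week 3, constant hazard |
|---|---|---|---|
| 15% | 26.3 | 6.9 | 7.3 |
| 25% (planned) | 43.8 | 11.5 | 12.7 |
| 35% | 61.3 | 16.0 | 18.7 |

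The first group could have no scheduled post-baseline chemistry on treatment. The others have an earlier value but no scheduled draw at stopping.

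**The case against.** **The evidence is a blank cell in a damaged table.** In the extracted text the DSIS row has lost its timing, the Nf-L row shows two marks in one cell, and some headers are garbled. A full cell count is no safeguard, because a lost mark leaves an empty cell behind. This stands, and it is why the source PDF must be checked first. Against it, the same gap appears in two rows in separate page segments, and neighboring laboratory rows kept their ETT marks.

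**Early stoppers can still be tested.** A reader might infer that these subjects have no end-of-treatment liver, renal or CK data at all. The documents do not support that. Section 11.5.2 provides for additional tests when clinically appropriate, and SAP Section 9.1 puts unscheduled values into the visit windows and the TE-period extremes. A stop shortly after Week 3 or Week 9 also has a nearby value. What remains is that discretionary testing depends on someone suspecting a problem, which a scheduled panel does not.

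**Bias is not shown.** A reader might conclude that the laboratory summary will look falsely clean. No document gives the timing of toxicity-related stops or the frequency of discretionary tests, so only a possible under-count can be claimed.

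**The count is a ceiling.** Subjects who withdraw consent have no further assessments, and those lost to follow-up give no sample, so an ETT mark would not recover their data. This stands.

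**Urinalysis carries little weight.** SAP Section 9.4.2 only lists it. This also stands.

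**Conclusion.** Subject to confirmation in the source, the schedule contains an unexplained gap: no protocol-scheduled chemistry at the ETT Visit, beside hematology, coagulation and HbA1c that are scheduled there. The visit-replacement rule could widen it. The effect is a possible under-count of abnormal chemistry among early stoppers in the TE-period threshold summaries.

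At most about 44 of 175 subjects are affected at 25% dropout. About 11 (even stopping) to 13 (constant hazard) would stop before the Week 3 draw; across 15% to 35% dropout the range is about 7 to 19. These figures assume that every dropout is a treatment discontinuation and that one of the two stopping patterns holds. The primary efficacy analysis is untouched.

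A separate, minor mismatch concerns vital signs. Section 11.5.3 states that "Vital signs assessments will be performed at Screening Visit 1 and at each clinic or home health visit", but Table 3-2 shows none at the Safety Follow-up Visit, which is a clinic visit. SAP Appendix A has no follow-up row for vital signs, so no planned by-visit summary at that visit depends on it. A reader might extend this to Screening Visit 2, but that is doubtful: the sentence names Screening Visit 1 on its own, which suggests that the later phrase is not meant to cover screening.

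**What to change.** 1. Check Table 3-2 in the source PDF. If the marks are there, the chemistry and urinalysis part of this point falls away, apart from the wording in step 3.
2. If the cells are blank, mark serum chemistry at the ETT Visit using the existing blood draw, and urinalysis as a lower priority. If the blanks are intended, state the reason.
3. State in Section 9.1.4 that an ETT Visit replacing a scheduled visit still includes that visit's chemistry.
4. Reconcile Section 11.5.3 with Table 3-2 on vital signs at the Safety Follow-up Visit.

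The cost is a table correction and a sentence or two of text, plus one tube and one urine sample per ETT Visit. The SAP needs no new window: chemistry shares the hematology windows, which run without a gap from post-dose Day 1 to Day 99, so an ETT value in that span falls into Week 3, 9 or 12.
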